## Statistical analysis

SPSS version 26 or newer will be used for the statistical analysis. Intention-to-treat analysis will be used. Little's Missing Completely at Random (MCAR) test will be used to evaluate whether data missing at the baseline, post-intervention and follow-up stages are systematically linked to included variables. Multiple imputation methods will be used to handle missing data. At the baseline session, the age and years of education will be compared between the groups using independent-samples *t*-tests. A chi-square test will be performed to evaluate differences in the proportions of men to women between the groups. Correlational analysis will be conducted between demographic variables (age, gender, and education) and primary and secondary outcomes at the baseline session. Variables with significant correlation will be regarded as potentially confounding variables.

A mixed repeated measures analysis of variance with the stimulation method (anodal/sham) as the between-subjects factor (independent variable) will be used to test differences in the dependent variables that include neurocognitive test scores, computer task accuracy ( $d'$ ) and reaction times at 3 time points (pre, post, and follow-up). The two ERP components (P550 and LPC) included in this analysis will be determined based on a visual inspection and findings from previous studies. The average ERP amplitudes at P500 will be determined at approximately 360 and 700 milliseconds after the stimulus, and the LPC will be determined at approximately 700 and 1,000 ms after the stimulus. The exact time windows used to calculate the average amplitudes will be adjusted based on the latency of the components in the actual data. To test the amplitudes of P550 and LPC, analyses (i.e., mixed repeated measures ANOVAs) will include stimulation method (anodal, sham)  $\times$  response (remembered, forgotten)  $\times$  time (pre, post, and follow-up). Significant interaction effects will be subjected to post-hoc analyses. Sensitivity tests that include potential confounders (i.e., demographic variables, primary and secondary outcomes) will be conducted to test the robustness of the outcomes. If any of the results do not meet the sphericity requirements, the Greenhouse-Geisser correction will be applied. The *p* levels of all post-hoc analyses will be adjusted using the Bonferroni correction (i.e.,  $p < 0.05/\text{number of comparisons}$ ). Only results that meet the corrected *p* value cut-off will be considered significant in the post-hoc analyses.

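### The SAP picks potential confounders by significant correlation with baseline scores, a criterion that does not match the stimulation-by-time test, and its two definitions of the confounder set disagree

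*SAP*

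**What the plan says.** Everything relevant is in the SAP, section Statistical analysis.

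- **The screen (first paragraph).** "Correlational analysis will be conducted between demographic variables (age, gender, and education) and primary and secondary outcomes at the baseline session". The rule that follows is "Variables with significant correlation will be regarded as potentially confounding variables". No significance level or multiplicity rule is given for it. The only multiplicity rule in the section is for follow-up tests: "The *p* levels of all post-hoc analyses will be adjusted using the Bonferroni correction".
- **Comparison of the arms at baseline (first paragraph).** "At the baseline session, the age and years of education will be compared between the groups using independent-samples *t*-tests", with a chi-square test for gender. Nothing links these tests to the choice of covariates.
- **The main model (second paragraph).** A mixed repeated measures ANOVA compares anodal with sham stimulation on the neurocognitive scores, task accuracy and "reaction times at 3 time points (pre, post, and follow-up"). No covariate is named. The baseline score enters as the first level of time. The ERP amplitudes have a further response factor (remembered or forgotten).
- **Where the confounders are used (second paragraph).** "Sensitivity tests that include potential confounders (i.e., demographic variables, primary and secondary outcomes) will be conducted to test the robustness of the outcomes".

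**The concern.** There are three linked problems and one separate one.

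1. **The screen looks at the wrong quantity.** Correlation with an outcome does not by itself make a variable a confounder of an arm comparison; the variable must also differ between the arms. Nor does correlation with the baseline level show that a variable predicts change, and the stimulation-by-time interaction is a comparison of change.
2. **The selection depends on chance.** Which variables pass depends on sample size and on a series of unadjusted tests, so the covariate set can differ from outcome to outcome for no substantive reason.
3. **The two paragraphs define the set differently.** The first limits it to demographics that reach significance. The second lists demographics without that limit and adds outcomes, with no time point. An outcome measured after stimulation may itself be affected by stimulation, and adjusting for it could bias the estimated effect.
4. **Separately, the baseline score is used inefficiently** in the main model.

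At stake are how much weight a finding of robustness can bear, whether the adjusted analysis is reproducible from the text, and some precision in the main comparison.

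**Working it through.** The SAP states no sample size, SD, effect size or correlation, so there is no figure of its own to reproduce. All inputs below are assumptions. Notation: N is the total sample, ρ the correlation between pre and post scores, and r_pre and r_post the covariate's correlations with the outcome at each visit. Variances are taken as equal across visits.

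**Step 1. How often a variable passes the screen.** Fisher z, two-sided 0.05: P(pass) ≈ 1 − Φ[(atanh r_crit − atanh r)·√(N − 3)], with a negligible opposite tail. For N = 40 and r = 0.3: (0.3228 − 0.3095) × √37 = 0.081, and 1 − Φ(0.081) = 0.47.

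| N | r_crit | Pass, true r = 0.2 | Pass, true r = 0.3 |
|---|---|---|---|
| 40 | 0.312 | 23% | 47% |
| 60 | 0.254 | 33% | 65% |
| 80 | 0.220 | 43% | 78% |
| 100 | 0.197 | 51% | 86% |

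If no variable is related to any outcome, the chance of at least one false flag over k independent tests is 1 − 0.95^k: 14% for k = 3, 37% for k = 9 and 54% for k = 15. Outcomes in one trial are correlated, so these are guides only.

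**Step 2. What the screened quantity says about change.** The covariate's correlation with change is (r_post − r_pre)/√(2(1 − ρ)).

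- Equal relation at both visits (r_pre = r_post): the numerator is 0, so the covariate removes 0% of the variance of change. If that common correlation is 0.3, the screen still passes it at the rates in Step 1.
- r_pre = 0, r_post = 0.3: the correlation with change is 0.3/√1.0 = 0.30 at ρ = 0.5 and 0.3/√0.4 = 0.474 at ρ = 0.8. It would remove 9% to 22.5% of the variance, but passes the screen only 5% of the time.

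**Step 3. How far a stable covariate moves the result.** Simulation, 4,000 runs per setting, two equal arms, effect 0.5 SD, covariate correlated 0.35 with the outcome at every visit. At N = 60, adding it to the comparison of change moves power from 0.477 to 0.468 (ρ = 0.5) and from 0.682 to 0.674 (ρ = 0.7). The estimate shifts by about 0.02 SD on average. The significance verdict changes in about 3% of runs, and in 1% to 5% over N = 40 to 100.

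**Step 4. The pre score as a covariate.** The variance relative to a change-score comparison is (1 − ρ²)/(2(1 − ρ)) = (1 + ρ)/2: 0.75 at ρ = 0.5, 0.80 at 0.6, 0.85 at 0.7 and 0.90 at 0.8. In the Step 3 simulation at N = 60, power rises from 0.48 to 0.59 (ρ = 0.5) and from 0.68 to 0.74 (ρ = 0.7).

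**Step 5. What demographics add after that.** The squared partial correlation with the post score given the pre score, when r is the same at both visits, is [(r − ρr)/√((1 − ρ²)(1 − r²))]². With r = 0.4 and ρ = 0.5 this is (0.2/√(0.75 × 0.84))² = 0.063. With r = 0.3 and ρ = 0.8 it is (0.06/√(0.36 × 0.91))² = 0.011. So demographics remove a further 1% to 6% of the residual variance. In the simulation, power becomes 0.60 and 0.75.

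**The case against.** Several points on the other side stand.

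- **A reader might infer that the robustness check is empty.** The document does not support that. The Step 2 result needs a similar correlation at every visit, about which the SAP says nothing. The second paragraph also lists outcomes among the confounders; if these are baseline values, the check has content. Even for a stable covariate, the verdict changed in 1% to 5% of simulated runs. The SAP does not state the form of the post-hoc analyses; if they compare the arms at a single visit, covariates related to level do matter.
- **A reader might infer that baseline information is never used in the main comparison.** It is used, as the pre level of time, only less efficiently than as a covariate. That loss comes from the form of the ANOVA and not from the screen. With 30 per arm, ρ = 0.6 and a stable covariate correlated 0.4 with level, simulation gives a variance ratio of 0.815 for the pre score alone and 0.79 with the covariate added.
- **A reader might infer that the plan intends to adjust for post-stimulation outcomes.** It does not say so. The bracketed list may be loose shorthand for the variables in the screen. The fault is that the wording leaves this open.
- **The consequence is limited.** The screen feeds sensitivity tests only, so a false flag leaves the main ANOVA and its type I error untouched. That ANOVA is a valid analysis, and preferring a baseline covariate is a matter of efficiency.
- **The variable unrelated to baseline but related to change is a constructed case.** Nothing in the SAP suggests that one exists.
- **Random allocation is not stated in the text at hand,** so the argument does not rest on it. Fixing the covariates in advance is sound either way.

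What remains is that the screen uses a criterion unrelated to its purpose, that its result varies by chance, and that the two definitions conflict.

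**Conclusion.** The point holds in this form. The screen tests association with baseline level, which indicates neither imbalance between the arms nor prediction of change. Its outcome is unstable at plausible sample sizes: 47% to 78% passing for a true correlation of 0.3 with N from 40 to 80. For a demographic with a stable relation to the outcome, agreement between adjusted and unadjusted stimulation-by-time results is close to built in, so it is weak evidence of robustness.

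The firmest defect needs no assumed numbers: the two paragraphs give different confounder sets, and the second admits outcomes with no time point.

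The efficiency point is separate. Using the pre score as a covariate would bring the variance to about 0.75 to 0.90 of the change-score variance for ρ from 0.5 to 0.8, with only a small further gain from demographics. These sizes rest on assumed N, ρ and covariate correlations, equal variances across visits, and a 0.05 level for the screen. The main analysis is not invalid; the change is worth making because it costs little.

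**What to change.** 1. Delete the significance screen and the sentence that turns significant correlates into confounders. Baseline correlations may stay as description.
2. Compare anodal with sham at post and follow-up by ANCOVA or a linear mixed model, with the pre-stimulation value of the same outcome as covariate. For ERP amplitudes, use the pre value for the same response condition, since each participant has one for remembered and one for forgotten items.
3. Add one fixed set of age, gender and years of education, the same for every outcome.
4. Report the unadjusted repeated measures ANOVA as the sensitivity analysis.
5. Reconcile the two definitions of the confounder set, and state that only baseline values, never post-stimulation outcomes, may enter as covariates.

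The cost is a change of SAP wording and 3 to 4 residual degrees of freedom (three demographics, plus the pre value). The plan already uses all of these variables, so no new data are needed.

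### Baseline is treated as an outcome level rather than a covariate, and anodal vs sham at post and follow-up is tested only after a significant interaction: valid, but inefficient

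*SAP*

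**What the plan says.** The second paragraph of the SAP's Statistical analysis section sets the main model as "A mixed repeated measures analysis of variance with the stimulation method (anodal/sham) as the between-subjects factor". The dependent variables are neurocognitive scores, task accuracy and reaction times "at 3 time points (pre, post, and follow-up"). The ERP model for P550 and LPC crosses stimulation, response and the same three time points. Baseline is therefore part of the outcome, and no main model has a baseline covariate.

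The only route to a comparison at one visit is this: "Significant interaction effects will be subjected to post-hoc analyses". Those tests are held to a Bonferroni-corrected threshold of 0.05 divided by the number of comparisons. Neither the set of comparisons nor their form (change from baseline, or raw values at a visit) is given.

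Covariates appear in one place: "Sensitivity tests that include potential confounders (i.e., demographic variables, primary and secondary outcomes) will be conducted to test the robustness of the outcomes". The first paragraph derives potential confounders from baseline correlations of age, gender and education with the outcomes: "Variables with significant correlation will be regarded as potentially confounding variables". Neither sentence says that each outcome's own baseline value is a covariate.

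**The concern.** When a baseline value correlates with later values, using it as a covariate gives a more precise group comparison than using it as a further outcome level. An interaction gate followed by Bonferroni tests adds a second hurdle. A real anodal effect could therefore be missed in data that would show it after baseline adjustment. A significant interaction F by itself does not show at which visit the groups differ, in which direction or by how much. Those answers depend on post-hoc tests whose form the SAP leaves open.

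**Working it through.** **Inputs.** From the SAP: two groups, three time points, Greenhouse-Geisser correction if sphericity fails, post-hoc tests after a significant interaction, Bonferroni. The SAP states no sample size, effect, SD or correlation, so it has no power figure to reproduce. Assumed: 30 per arm, random allocation, complete data, normal outcomes with SD 1, peak effect 0.5 SD, pre-post correlation ρ = 0.5, 0.7 or 0.8.

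**Precision at one visit, closed form (n per arm).**
- Change from baseline: variance = (2/n) × 2(1 − ρ)
- Baseline-adjusted: variance = (2/n) × (1 − ρ²)
- Ratio = 2/(1 + ρ) = 1.33, 1.18, 1.11 for ρ = 0.5, 0.7, 0.8
- Raw difference at a visit relative to baseline-adjusted: 1/(1 − ρ²) = 1.33, 1.96, 2.78

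Simulated standard errors at post are 0.225/0.185/0.156 (adjusted) against 0.257/0.199/0.163 (change). The adjusted ones are 12%, 7% and 4% smaller.

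**Power by simulation (20,000 trials per cell, same correlation between all pairs of visits).** Gated route: interaction F at 0.05, then between-group tests of change at post and follow-up, 0.025 each. Planned route: two ungated baseline-adjusted contrasts, 0.025 each. For these two routes, success means at least one significant visit. Entries are % for ρ = 0.5/0.7/0.8.

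| Effect in SD (post, follow-up) | Interaction F alone | Gated route | Planned contrasts | Gain over gated (points) |
|---|---|---|---|---|
| Sustained (0.5, 0.5) | 49.0/72.4/88.7 | 47.3/71.1/87.9 | 66.3/81.9/92.9 | 19.0/10.8/5.0 |
| Decaying (0.5, 0.25) | 38.2/59.4/77.4 | 34.9/56.5/75.3 | 51.1/67.9/82.4 | 16.2/11.4/7.1 |
| Post only (0.5, 0) | 49.0/72.2/88.8 | 35.2/57.0/77.0 | 47.9/65.6/81.8 | 12.7/8.6/4.8 |
| Late (0.25, 0.5) | 37.8/58.6/78.1 | 34.6/55.5/76.0 | 50.8/67.4/83.0 | 16.2/11.9/7.0 |
| None | 5.0/4.9/4.8 | 3.4/3.4/3.3 | 4.6/4.7/4.7 | – |

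**Source of the gain (sustained effect).** Ungated change tests have 52.0/74.6/89.8% power. Dropping the gate therefore gives 4.7/3.5/1.9 points, and baseline adjustment a further 14.3/7.3/3.1.

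**Other settings.**
- Correlation fading over time (ρ for adjacent visits, ρ² for pre to follow-up): gain 9.0 to 22.5 points.
- 20 or 40 per arm, equal correlations: gain 2 to 19 points.
- Post-hoc tests on raw values at each visit, sustained effect: gated power falls to 32/38/42% against 66/82/93%. That is a loss of about 34 to 51 points, and it grows with ρ.

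**The case against.** The strongest reply is that the plan states a coherent and valid route, so the point is a preference for efficiency and not an error. That is right, and the point claims no more. Validity here refers to the group-by-time test. The SAP does not name that test as the one that carries the treatment claim. If a significant group main effect or a significant interaction could each count, the error would be 1 − 0.95² = 9.75%.

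Further objections, and what stands of each:

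- **Unequal error rates.** The gated route spends about 3.4% and the planned contrasts about 4.7%. With the contrasts cut back to the gated error (about 0.018 per visit), the gain falls to about 13 to 2 points for a sustained effect and about 7 to 0 for post only. This stands as a measure of size. Leaving alpha unspent is, however, itself a consequence of the gate.
- **The ranking can reverse.** For a post-only effect, the interaction F alone beats the planned contrasts by about 1 to 7 points (up to about 10 at 20 per arm). This stands. The F alone does not locate the effect, and once the SAP's post-hoc step is applied, its power is below that of the contrasts in every pattern in the table.
- **Assumed inputs.** Sample size, correlation, effect pattern and post-hoc form are mine. This stands; change scores are the assumption more favourable to the plan.
- **Adjustment may already be intended.** The mention of primary and secondary outcomes in the sensitivity sentence could mean baseline adjustment. It does not say so, and it does not alter the main analysis.
- **The primary time point may be in the protocol.** It may be. The point rests on the model and the gate, both of which the SAP itself fixes.
- **ERP outcomes were not simulated.** Correct: no gain is quantified for P550 or LPC.

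**Conclusion.** The point holds as an inexpensive improvement that should be made; it is not a flaw in validity. Under the stated assumptions with 30 per arm and equal correlations, the SAP's route gives up 5 to 19 points of power to show an effect at one visit or more. At matched error rates the figure is about 0 to 13. The loss shrinks as the pre-post correlation rises if post-hoc tests use change scores, and is much larger if they use raw values. The direction is well supported. The size is uncertain, because the SAP gives none of the inputs that determine it.

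**What to change.** For each behavioural outcome, model the post and follow-up values with stimulation, visit, stimulation × visit, baseline value and baseline × visit, as a linear mixed model or as an ANCOVA at each visit. Name anodal minus sham at post and at follow-up as the two planned contrasts. Share alpha between them (0.025 each, or Holm), do not gate them on the interaction, and report both estimates with 95% confidence intervals. For P550 and LPC, add response as a within-subject factor and the matching pre-intervention amplitude as covariate. Keep the three-time-point ANOVA as a supportive analysis.

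The change costs SAP wording and different model syntax, with no further data or participants. It assumes random allocation and a roughly linear relation with baseline. It also accepts somewhat less power than the interaction F alone if the effect is confined to the post visit.

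### Could the sensitivity tests end up adjusting for outcomes measured after stimulation?

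*SAP*

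**What the plan says.** Three statements in the SAP, section Statistical analysis, bear on this.

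- The first paragraph sets up a screen: "Correlational analysis will be conducted between demographic variables (age, gender, and education) and primary and secondary outcomes at the baseline session". It then draws the consequence: "Variables with significant correlation will be regarded as potentially confounding variables".
- The second paragraph sets out the main analysis, a mixed repeated measures ANOVA comparing anodal with sham stimulation. Its dependent variables include neurocognitive scores, task accuracy and "reaction times at 3 time points (pre, post, and follow-up". The ERP amplitudes are analysed over the same three times.
- Later in the second paragraph comes the robustness check: "Sensitivity tests that include potential confounders (i.e., demographic variables, primary and secondary outcomes) will be conducted".

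The SAP gives no sample size, effect size or correlation between outcomes.

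**The concern.** The sentence on sensitivity tests lists outcomes as covariates without saying when they are measured, and two of the three measurement times come after stimulation has begun to act. Taken literally, a post or follow-up score on one test could be used to adjust the comparison on another.

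That would be a real error. A covariate that stimulation can change carries part of the stimulation effect. Holding it constant removes that part from the estimate. If the analysed outcome is in truth unaffected, the adjustment produces an apparent effect in the opposite direction. Because the check exists to test robustness, a sound main result could look fragile only because of the adjustment. Values taken before stimulation do not carry this risk.

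**Working it through.** **Step 1: the text.** The SAP states no figure to reproduce, so the first check is to compare possible readings of the covariate set with both paragraphs.

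| Reading | Fits the baseline screen (first paragraph)? | Fits the parenthesis (second paragraph)? | Post-stimulation covariate? |
|---|---|---|---|
| A. Only demographic variables that pass the screen | Yes | No, outcomes are listed too | No |
| B. Demographic variables and baseline outcomes that pass the screen | Yes | Yes | No |
| C. Demographic variables and outcomes at any time | No, later values are never screened | Yes | Yes |

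Only B fits both paragraphs. The term for confounders in the second paragraph takes up one introduced in the first, and the parenthesis repeats the two groups in the screen in the same order. The screen refers to variables in general, so it can cover both sides of a significant correlation. The reference to three time points describes dependent variables and says nothing about covariates. Reading C would also need a rule for choosing among later values, and the SAP has none.

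**Step 2: what reading C would cost.** All inputs are assumed:

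- within-arm SDs of 1;
- a true effect of 0.5 SD on change in the analysed outcome and 0.5 SD on each covariate outcome;
- pre-post correlation r = 0.6;
- between-outcome correlation ρ = 0.3, 0.5 or 0.7;
- correlation across both time and outcome of r × ρ;
- a covariate that is allowed to act on change.

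The slope of change (post minus pre) on one post-stimulation covariate is ρ − rρ = ρ(1 − r) = 0.4ρ. The adjusted effect is 0.5 − 0.5 × 0.4ρ:

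- ρ = 0.3: 0.5 − 0.06 = 0.44
- ρ = 0.5: 0.5 − 0.10 = 0.40
- ρ = 0.7: 0.5 − 0.14 = 0.36

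The loss is 0.06/0.5 = 12% to 0.14/0.5 = 28%. If the analysed outcome is unaffected, the false effect is −0.06, −0.10 or −0.14 SD.

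With k such covariates the summed slope is k × 0.4ρ / (1 + (k − 1)ρ). For k = 3 and ρ = 0.5 this is 0.6/2 = 0.30, so the adjusted effect is 0.5 − 0.5 × 0.30 = 0.35.

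**Step 3: a different contrast.** If the post score is analysed instead of change, the adjusted effect is 0.5 − ρ × 0.5 = 0.35, 0.25 and 0.15 for the same three correlations. A simulation with 200,000 per arm gave 0.354, 0.253 and 0.151.

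**Step 4: reading B.** Stimulation has no effect on a baseline covariate, so the subtracted term is slope × 0 = 0 and the effect stays at 0.50. The same simulation gave 0.503, 0.503 and 0.499. This assumes that the groups do not differ systematically at baseline.

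**The case for a change.** The best case for a change is that the baseline qualifier is attached to the screening correlation and not to the covariates themselves. A screen selects which variables qualify; strictly, it does not fix the time at which a selected outcome enters the model. Nor does the SAP say whether the demographic variable, the outcome or both become covariates. Two analysts could therefore fit different sensitivity models, possibly after seeing results, and one or two sentences would settle it.

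Part of this stands. The wording is loose, and the bias under reading C is real in direction. But the choice that the text leaves open in earnest lies between readings A and B, and neither includes anything measured after stimulation. Reaching C means setting aside the sentences that introduced the term. It also means using a covariate that a trial analyst would normally avoid. For harm to follow, someone must then let that sensitivity result outweigh a main analysis it does not touch.

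A related point is that an outcome's own pre value is already a level of the time factor, so entering it as a covariate in the same model would be redundant. That is a separate modelling matter which an analyst would meet and handle when fitting the model. It does not turn the missing qualifier into a defect.

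**Conclusion.** No change is needed. The SAP omits a word that its own first paragraph supplies, and the reading that fits both paragraphs gives a valid adjustment. The possible distortion is 0.06 to 0.14 SD out of 0.5 with one post-stimulation covariate when change is analysed, and 0.15 to 0.35 SD when the post score is analysed. It arises only under a reading that the SAP does not plan. The wide gap between those two ranges shows how far the size depends on assumed inputs; the SAP offers none of its own. The main comparisons of anodal with sham stimulation are the same under every reading. This is a gap that analysts can be expected to fill sensibly by using baseline values.

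### Within each outcome, Holm's step-down in place of plain Bonferroni would keep the same family-error bound after a significant interaction and never reject less

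*SAP*

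**What the plan says.** The section Statistical analysis specifies a mixed repeated measures ANOVA "with the stimulation method (anodal/sham) as the between-subjects factor" for neurocognitive scores, task accuracy and "reaction times at 3 time points (pre, post, and follow-up"). The ERP amplitudes get a larger model that adds "response (remembered, forgotten") as a third factor.

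Two rules follow in series. The entry rule is: "Significant interaction effects will be subjected to post-hoc analyses". The threshold rule is that the p "levels of all post-hoc analyses will be adjusted using the Bonferroni correction", that is, 0.05 divided by the count of comparisons. Only results below that corrected p "value cut-off will be considered significant in the post-hoc analyses".

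The section does not state the level of the interaction test, which comparisons make up the post-hoc set, or how many there are. It gives no sample size, effect or correlation.

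**The concern.** The interaction test already screens out most chance findings before any post-hoc test is run, and a full Bonferroni division is then applied on top. For some post-hoc sets the two steps together run well under the 5% they are meant to hold, and power is lost on the contrasts that say whether stimulation helped after treatment and whether the benefit lasted. A step-down method gives part of that power back at no cost in error control. A well-chosen set of contrasts gives back more.

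**Working it through.** **Inputs.** From the SAP: two arms, three visits, a significant interaction required, then 0.05/m for m comparisons. Assumed, because the SAP gives none: interaction tested at 0.05; 30 per arm; within-person correlation 0.6; anodal-sham difference 0.65 SD at post and follow-up. The plan states no power or error rate, so there is no figure to reproduce.

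**Step 1: price of dividing by m, for a single test and ignoring the interaction step.** If a test has 80% power at two-sided 0.05, its mean z is 1.960 + 0.842 = 2.802. Power at 0.05/m is Φ(2.802 − z), with z the two-sided critical value at 0.05/m.
- m = 2: Φ(2.802 − 2.241) = 71.2%
- m = 3: Φ(2.802 − 2.394) = 65.8%
- m = 6: Φ(2.802 − 2.638) = 56.5%

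**Step 2: why Holm costs nothing in error control.** Holm compares the smallest p with 0.05/m, the next with 0.05/(m−1), and so on, stopping at the first failure. It holds family error at 5% for any m and any dependence. Requiring a significant interaction beforehand can only remove rejections. No Holm threshold is below 0.05/m, so every Bonferroni rejection is also a Holm rejection.

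**Step 3: why one particular set needs no division.** Let d1, d2, d3 be the anodal-sham differences at pre, post and follow-up. The interaction null is d1 = d2 = d3. The three differences in change are d2−d1, d3−d1 and d3−d2. If two of these are zero, so is the third. Hence, once the interaction null is false, at most one of the three is a true null. The 5% interaction test covers the complete null, and a single 5% test covers the one remaining null. This is a closed procedure.

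**Step 4: simulation for that set** (20,000 trials per scenario, each contrast a two-sample t-test on change scores; interaction significant in 83%).

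| | Bonferroni | Holm | 0.05 each after the interaction |
|---|---|---|---|
| Power per true contrast | 63% | 67% | 75% |
| Power to show both pre-post and pre-follow-up | 47% | 54% | 66% |
| Power for at least one true contrast | 79% | 79% | 83% |
| Family error, one true null left | 1.6% | 3.2% | 4.9% |
| Family error, complete null | about 4% | about 4% | about 5% |

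Holm gains nothing in the third row because its first threshold is Bonferroni's. If the effect fades (0.65 then 0.33 SD), power for the pre-follow-up contrast is 15%, 19% and 27%.

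**Step 5: sensitivity to the assumptions.** With 40 per arm and 0.63 SD, per-contrast power in the same column order is 64%, 67% and 75% at correlation 0.5, and 88%, 90% and 94% at 0.7. With 30 per arm, 0.65 SD and correlation 0.8, Bonferroni gives 93% and the uncorrected closed test 97%.

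**Step 6: sets for which the correction must stay.** For arm differences by visit, if only post differs, pre and follow-up are both true nulls while the interaction null is false. Were the two tests independent and the interaction always significant, uncorrected family error would be 1 − 0.95² = 9.75%. Simulated with the main inputs but the effect at post only, it is 7.3% uncorrected against 2.4% with Bonferroni. Other scenarios with only post differing give 7.5–9.6% against 2.7–3.5%. Six within-arm time comparisons give 13–17% against 2.4–3.3%. Holm stays at or below about 5% in all of these; the simulation standard error near 5% is √(0.05 × 0.95/20,000), or 0.15 points. The three-way ERP model was not simulated.

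**The case against.** The strongest reply is that the plan contains no mistake: Bonferroni after a significant interaction is valid, familiar and easy to report. That stands, and it sets the level of this point.

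Three stronger readings might be inferred, and the document supports none of them.

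- **That Bonferroni adds no error control here.** This is true only in the sense that 5% is already held if the post-hoc set is exactly the three differences in change. The SAP never names its set. For arm differences by visit or within-arm comparisons, both ordinary follow-ups to an interaction, the correction does real work. The argument that at most one contrast can be null does not carry over to the ERP model.
- **That the plan loses 12 points of power.** The difference 75 − 63 = 12 belongs to one assumed scenario. For the same contrasts it is 6 points at correlation 0.7 with 40 per arm, and about 4 at 0.8 with 30 per arm. For finding at least one true contrast it is 83 − 79 = 4 points.
- **That a real effect will often give a significant interaction with no significant contrast.** For the change contrasts in the main scenario this happened in about 4% of simulated trials.

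It is also fair to say that Holm alone gains little: about 2 to 4 points per change contrast at the assumed effects, and 0 to 3 for arm differences by visit. But the gain costs almost nothing.

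**Conclusion.** A cheap, optional improvement. The post-hoc rule is valid but more conservative than needed. The case for Holm is general: it needs no assumption about sample size, effect, correlation or the choice of comparisons. The case for uncorrected 5% tests is conditional. It requires two arms, three visits, an interaction test that itself holds 5%, and a post-hoc set fixed in advance as exactly the three differences in change. The size is illustrative: about 4 points per contrast from Holm and 12 from the closed procedure in the main scenario, and less where power is already high. The point concerns comparisons within one outcome and does not address multiplicity across outcomes.

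**What to change.** 1. Replace the Bonferroni rule with Holm's step-down for all post-hoc families, including those from the three-way ERP models, and name the comparisons and their number for each outcome.
2. Optionally, for the two-arm, three-visit outcomes, fix the post-hoc set as the three anodal-sham differences in change (pre to post, pre to follow-up, post to follow-up). State that the interaction is tested at 0.05 and that, if it is significant, each contrast is tested at 0.05 as a closed procedure.
3. State that arm differences by visit, within-arm comparisons and ERP contrasts keep a multiplicity correction (Holm).

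The cost is one or two sentences. Holm needs only the p values that SPSS prints, put in order. The downside is that no simple simultaneous confidence intervals match Holm or the closed procedure, so unadjusted 95% intervals would be shown beside the decisions and labelled as such.
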